Despite our advances in understanding the pathophysiology of IBS, there are still **unmet needs** in terms of treatment options. Rifaximin is a non-absorbable antibiotic that has been shown to improve symptoms in the diarrhea-predominant subtype of IBS (IBS-D) (31,32). However, mechanisms by which rifaximin leads to improvement in IBS-D are still unknown. In vitro studies suggest that rifaximin may prevent changes in barrier dysfunction and reverse mucosal inflammation by modulating bacteria in the small intestine (33). Conversely, prior studies have not demonstrated significant effects of rifaximin on fecal microbial composition (34,35). This is likely because rifaximin is insoluble in the colon and has antimicrobial effects primarily in the small bowel (36). Furthermore, rifaximin leads to improvement in symptoms in *only 40% of IBS patients* with a therapeutic gain of 9% over placebo. Because of these observations, one could argue that rifaximin may be effective only in those IBS patients who have concomitant SIBO. Indeed, a recent study demonstrated that those IBS patients with SIBO had a significantly increased response to rifaximin compared with those IBS patients without SIBO (37).

Dietary modification has also been advocated as a potential treatment option in IBS-D. The vast majority of IBS patients believe certain foods trigger their IBS symptoms (38). Fermentable oligosaccharides, disaccharides, monosaccharides, and polyols (FODMAP) are short-chain, poorly absorbable carbohydrates. Recently, a diet low in FODMAP has been shown to improve symptoms in up to 76% of IBS patients (39,40). However, two recent randomized controlled trials failed to show a low FODMAP diet was superior to traditional IBS dietary advice in controlling symptoms (41,42). Furthermore, improvement in symptoms was reported by *only 50% of patients on low FODMAP diets*. Moreover, the exact mechanism by which a low FODMAP diet improves symptoms in IBS is still unknown. It is postulated that the gut microbiota are critical in generation of symptoms in the presence of dietary FODMAPs and lead to production of gases, including hydrogen, CO₂, and methane. This may generate symptoms in IBS particularly in the setting of visceral hypersensitivity (43).

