- d) Other outcomes that will be assessed include differences in tryptophan hydroxylase-1 (TpH-1) and sucrase-isomaltase single nucleotide polymorphisms (SNPs) in different cohorts of IBS-D patients.

Aim 3: Develop a predictive model to identify subsets of IBS-D patients responsive to treatment.

- a) We will develop and validate a predictive model of response to low FODMAP diet using data from the subjects randomized to a low FODMAP diet (Aim 1) combined with existing data from a separate cohort of IBS-D subjects previously treated with a low FODMAP diet (HUM 00053274).

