We will develop and validate a predictive model of response to low FODMAP diet using data from the subjects randomized to a low FODMAP diet (Aim 1) combined with existing data from a separate cohort of IBS-D subjects previously treated with a low FODMAP diet (HUM 00053274).

3B. Experimental Methods:

We will use the combined cohort of patients treated with a low FODMAP diet (Aim 1 and HUM #00053274), which will be split into a training set from a random sample of 80% of the data while the remaining 20% of the data will serve as the test set. Using a random forest model, 5x2 nested cross-validation (CV) will be performed within the training set for model selection and hyperparameter tuning. The candidate models will be compared by testing for overlap of confidence intervals for area under the curves (AUCs, two-sided test). Once a final model is selected, model performance will be evaluated on the test set.

Study Timeline:

Figure 1 IBS Subject Timeline

Schedule of Events - Low FODMAP Group

Visit Number	Pre-Visit	Visit 1	Visit 2	Visit 3	Visit 4	Visit 5
Visit Description	Pre-screening (Phone/in person)	Baseline (Phone/in person)	Monitoring (Phone/in person)	Monitoring (Phone/in person)	Monitoring (Phone/in person)	Monitoring/Outcomes (Phone/in person)
Time point	Eligibility	Day 0	Day 7±3 days	Day 14±3 days	Day 28±3 days	Day 35±3 days
7 day pre-screening questionnaire	X					
Informed Consent	X					
Medical History /Physical Examination		X	X	X	X	X
Urine pregnancy test (Females of childbearing age)		X				
Washout	X					
Questionnaires		X		X		X

3-day food diary		X				
24-hour dietary recall			X	X	X	X
GI nutrition consultation		X		X		
Colonoscopy with mucosal biopsies (optional)	X					
Serum Cytokine Profiles (optional)		X				X
Buccal swab collection (optional)		X				
Glucose hydrogen breath testing		X				X
Stool collection for fecal microbial analysis		X (3 baseline samples)		X	X	X
Randomization	X					
Dietary Compliance			X	X	X	X
Adverse Events Monitoring			X	X	X	X

*Female participants capable of bearing children will be required to attend visit 1 in person for the pregnancy test

*During COVID-19 pandemic, all hydrogen breath tests will be conducted remotely

Schedule of Events – Rifaximin Group

*Female participants capable of bearing children will be required to attend visit 1 in person for the pregnancy test

*During COVID-19 pandemic, all hydrogen breath tests will be conducted remotely

Visit Number	Pre-Visit	Visit 1	Visit 2	Visit 3	Visit 4	Visit 5

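### Aim 3 tests its diet-response model only on a random 20% of two pooled cohorts, so it would not show whether the AUC partly reflects cohort differences or whether the model carries over between studies

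*Combined protocol and SAP*

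**What the plan says.** Section 6, Specific Aim 3, states the goal: "We will develop and validate a predictive model of response to low FODMAP diet". The data are the trial's low FODMAP arm together with "existing data from a separate cohort of IBS-D subjects previously treated with a low FODMAP diet"; section 2, Aim 3(a), says the same. Under 3B the two sources become one combined cohort, "which will be split into a training set from a random sample of 80% of the data", and "the remaining 20% of the data will serve as the test set". A random forest is tuned by 5x2 nested cross-validation inside the training set, candidate models are compared on AUC, and the chosen model is then evaluated on the test set.

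Neither section mentions a cohort term, a split stratified by cohort, a batch adjustment, an AUC within each cohort, or training on one cohort and testing on the other. For the older cohort the documents give no size, response rate, responder definition, entry criteria or assay. They do not list the Aim 3 predictors.

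**The concern.** A pooled AUC is the proportion of responder/non-responder pairs that the model ranks correctly, and some of those pairs take one patient from each cohort. Suppose one cohort responds more often and the predictors carry a mark of the cohort, for example through sampling, sequencing or questionnaires. The model can then rank many cross-cohort pairs correctly just by recognising the study. A random split puts both studies into training and test, so the hold-out does not remove this credit.

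The hold-out also cannot show whether the model works in patients from a different study, which is what a reader may take validation to mean. The plan has two cohorts in hand and could examine this directly.

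**Working it through.** Aim 3 states no target AUC, sample size or power, so there is no planned figure to reproduce. The checks below measure how large the effect could be.

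**Inputs from the documents.** Section 1 cites improvement "has been shown to improve symptoms in up to 76% of IBS patients" and also in "only 50% of patients on low FODMAP diets". Section 10 plans on 60% responders. The diet arm is about 100 if 200 patients are randomised 1:1 (sections 2 and 6), or 32 according to section 10.

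**Assumptions.** The older cohort's size is unknown. Pairing these response rates across the two cohorts is illustrative; no rate is reported for the older cohort.

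**1. Upper bound: a model that knows only the cohort.** Let cohort B have the higher response rate. Then AUC = (1 + TPR − FPR)/2, where TPR and FPR are cohort B's shares of responders and of non-responders. With equal cohort sizes:

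| Response A v B | TPR | FPR | AUC |
|---|---|---|---|
| 60% v 60% | 0.500 | 0.500 | 0.50 |
| 50% v 60% | 0.60/1.10 = 0.545 | 0.40/0.90 = 0.444 | 0.55 |
| 60% v 76% | 0.76/1.36 = 0.559 | 0.24/0.64 = 0.375 | 0.59 |
| 50% v 76% | 0.76/1.26 = 0.603 | 0.24/0.74 = 0.324 | 0.64 |

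With a 70:30 mix either way, the last pair gives 0.61 to 0.63. The AUC within each cohort is 0.50 in every row.

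**2. A fitted forest with no true signal.** Simulation with 100 patients per cohort, 80% of them for training, 30 features of which 10 are shifted by 1 SD between cohorts, and no relation to response within a cohort. Tuning was not simulated.

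| Response A v B | Feature shift | Pooled AUC | Within-cohort AUC | Cross-cohort AUC |
|---|---|---|---|---|
| 60% v 60% | 1 SD | 0.502 | 0.501 | 0.496 |
| 50% v 60% | 1 SD | 0.509 | 0.497 | 0.505 |
| 60% v 76% | 1 SD | 0.537 | 0.504 | 0.498 |
| 50% v 76% | 1 SD | 0.583 | 0.499 | 0.503 |
| 50% v 76% | none | 0.502 | 0.500 | 0.496 |

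The forest falls short of the upper bound (0.583 against 0.639 at 50% v 76%). The effect vanishes if rates are equal or if the features do not reveal the cohort. The within-cohort and cross-cohort AUCs stay near 0.50 throughout, so they would detect the problem.

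**3. A model with real signal.** Binormal simulation, 100 per cohort, score = logit(cohort response rate) + d·x − d²/2 with d = √2·Φ⁻¹(within-cohort AUC). A true within-cohort AUC of 0.65 becomes a pooled AUC of 0.66 at 50% v 60%, 0.68 at 60% v 76% and 0.71 at 50% v 76%. A true 0.75 becomes 0.754, 0.764 and 0.786.

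**4. Could the planned test AUC reveal this?** Hanley-McNeil 95% half-widths at AUC 0.65 with 60% responders and an assumed older cohort of 50:

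- Diet arm 100: pool 150, test set 30 (18 responders, 12 non-responders), half-width 0.20.
- Diet arm 32: pool 82, test set 16 (10 and 6), half-width 0.28.

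The largest rise in step 3 is 0.71 − 0.65 = 0.06, far inside that error. By contrast, testing on a whole diet arm of 100 (60 and 40) gives a variance of [0.2275 + 59 × 0.0590 + 39 × 0.0896]/2400 = 0.0030 and a half-width of 1.96 × 0.055 = 0.11.

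**The case against.** A reader might infer that the test AUC will be inflated. The documents do not support that. Inflation needs both a difference in response rates and predictors that reveal the cohort, and neither is shown. The 50% and 76% are general literature rates, one of them a maximum; neither is attributed to HUM 00053274 or forecast for this trial. At a gap of 50% v 60% the effect on a real model is about 0.01.

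A reader might also infer that the plan promises external validation and fails to deliver it. It does not: nested cross-validation with a held-out 20% is a recognised internal validation, and the word external is not used. The description in section 3 of a linking list held by the investigators suggests that the older cohort may be local. Cross-cohort testing would then be mainly validation over time at one institution.

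Nor should pairs that cross cohorts be barred from the analysis. The trial has its own symptom threshold and excludes prior formal dietary education (section 4). If the cohorts differ in severity and severity affects response, that is legitimate predictive information, and dropping those pairs would discard it.

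Finally, Aim 3 does not touch the primary outcomes of Aims 1 and 2, and the imprecision of the test AUC is a larger weakness than the possible inflation.

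All of this stands. What remains is that the plan has no check on cohort effects, that its own result could not reveal one, and that the data for a check are already available.

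**Conclusion.** The point holds in conditional form. As written, validation in Aim 3 means internal validation on one mixture of two studies. If response rates differ and the predictors reveal the cohort, the pooled test AUC could overstate discrimination within a cohort. With equal cohort sizes, cohort recognition alone can reach at most 0.55 at 50% v 60% and 0.64 at 50% v 76%. A forest would probably give less, and the inflation is zero if either condition fails. These figures rest on assumed response rates and cohort sizes, because the documents describe neither for the older cohort.

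This is an inexpensive improvement worth making before analysis. It is not an internal contradiction, and it does not show that the planned model would fail.

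**What to change.** Keep the pooled final model and the planned 20% hold-out. Stratify the split and the cross-validation folds by cohort and response; this balances the sets but does not by itself remove a cohort effect. Then prespecify two further reports:

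1. Train on HUM 00053274 and test on the trial's diet arm, and the reverse.
2. Give the AUC within each cohort, and their average, beside the pooled AUC, with confidence intervals.

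Claim validation across studies only from report 1. State the older cohort's size, response rate, responder definition, entry criteria and assay, so that a reader can judge whether either condition for inflation is met.

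The cost is a few more model fits and a paragraph of SAP text, with no new patients or samples. The reported AUC may be lower, and estimates will be imprecise if either cohort is small: with a diet arm of 32 (19 responders, 13 non-responders) the half-width at AUC 0.65 is about 0.19, since [0.2275 + 18 × 0.0590 + 12 × 0.0896]/247 = 0.0096 and 1.96 × 0.098 = 0.19.

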6 STUDY DESIGN AND PROCEDURES

Specific Aim 1: Randomize IBS-D subjects to receive either a nonabsorbable antibiotic rifaximin vs. low FODMAP dietary intervention.

1A. Research Approach:

200 IBS-D subjects will be carefully phenotyped using validated questionnaires (IBS symptoms, stool form, psychological function, quality of life) and diet analysis. IBS-D subjects will also undergo baseline testing including GHBT as well as fecal microbial analysis. IBS-D subjects will then be randomized to receive either rifaximin or low FODMAP diet intervention at the initial screening visit. Efficacy of therapies will be monitored with validated questionnaires to track symptomatic improvement. The primary outcome will be changes in mean daily pain or bloating after intervention compared with baseline. Responders to intervention will be defined as $\geq 30\%$ reduction in mean daily pain or bloating by visual analog scale (VAS) compared with baseline. Secondary outcomes will monitor changes in IBS-Symptom Severity Score as well as differences in GI symptoms, stool form, psychological function, quality of life, and dietary intake before and after intervention.

1B. Experimental Methods:

Subject Recruitment: 200 adult subjects ≥ 18 years of age who meet Rome IV criteria for IBS-D will be enrolled in the study. Women of childbearing age will undergo a urine pregnancy test to exclude the possibility of pregnancy. Women who are breastfeeding will also be excluded. IBS-D subjects will be excluded if they have underlying celiac disease, inflammatory bowel disease, or other organic disease that could explain their symptoms. All IBS-D subjects will have prior sigmoidoscopy or colonoscopy with mucosal biopsies within the past 2 years to rule out microscopic colitis. IBS-D subjects with a history of GI tract surgery, except for appendectomy, will also be excluded from the study. Antibiotics taken within 3 months prior to enrollment will not be permitted (54). IBS-D subjects on probiotics must discontinue their use at least 1 month prior to fecal collection. IBS medications, including anti-depressants, will be allowed if the dose has been stable for at least 1 month before inclusion. Medications will be carefully tracked to follow any potential confounding issues. IBS-D subjects who have previously received formal

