10 STATISTICAL CONSIDERATIONS

Aim 1:

All of the interventional analyses will be analyzed on an intention-to-treat basis. Each IBS-D subject will act as his/her own control for analysis of the effects of either rifaximin or low FODMAP diet intervention. This paired design inherently eliminates a significant amount of bias/confounding and affords increased statistical power. We will power our study to detect a $\geq 30\%$ improvement in mean daily bloating or abdominal pain after intervention compared with baseline. Using available data from a US study on low FODMAP diet in IBS patients (42), we conservatively estimate that we will require 14 IBS-D subjects in each arm to have $>90\%$ power to detect a mean difference of 1.7 in abdominal bloating scores after intervention via paired t-tests with the expected standard deviation (SD) of ± 1.8 . Thus, our expected enrollment of 32 IBS-D subjects in each arm will be more than sufficient for analyzing this aim (see biostatistical analysis for Aim 2), even if the SD is nearly two-fold larger than expected.

Aim 2:

We will examine both inter- and intra-individual variability in microbiota-derived metrics. We plan to use a paired design to eliminate a significant amount of bias/confounding and increase statistical power. We anticipate that there will be some variability in the three samples collected prior to treatment, and various techniques will be employed to average these data so they are incorporated as the baseline. For example, for α diversity (Shannon index) a simple average of the three time points will be sufficient to

establish a baseline α diversity. Similar techniques will be applied to other community structure metrics, to create “deltas” between post-treatment time points and the baseline.

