These microbe-derived metrics and accompanying clinical variables will be initially analyzed through descriptive statistics before/after intervention. Histograms and measures of frequency or central tendency/spread will be used to optimize variable constructions. Subsequently, initial bivariable longitudinal analyses in an inter-individual fashion (assessing group-wide trends before/after intervention) that also account for the paired nature of the data (intra-individual) will be employed for categorical data (McNemar’s test) and continuous data (paired t-test), or their non-parametric equivalents for data not normally distributed. Multiple comparisons will be made for individual OTU abundance metrics, with a focus on the most abundant taxa. However, we will avoid a high false discovery rate through use of linear discriminant analysis effect size (LEfSe) analysis (70). Similar to Aim 1, we will power our study using a paired t-test based on the primary outcome to detect a change in diversity at the end of the intervention compared with baseline. In addition, we will also examine intermediate endpoints or longitudinal trends over time to determine if these are important. If this is the case, we will also use mixed model analyses with repeated measures.

Although this work is exploratory, we wanted to ensure that we will have sufficient power to detect notable differences in microbial and functional characteristics with our planned recruitment base. Based on prior studies with low FODMAP diet in IBS patients (42,45,71), we conservatively estimate that 60% of IBS-D subjects will respond to treatment. We further expect that only those IBS-D subjects who respond to a low FODMAP diet will show changes in fecal microbial diversity. Given our sample size of 32 subjects per arm, we will have >90% power to detect a mean difference ≥ 0.4 in θ_{YC} (a measure of β -diversity) between responders and non-responders. As we are already seeing differences in θ_{YC} of this magnitude or greater, this suggests we are appropriately powered to detect meaningful differences in the microbiota between groups even if our standard deviation is 2-fold greater than expected.

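### Aim 3 compares candidate models by whether their AUC confidence intervals overlap; the models share subjects, so the rule is far too conservative on the natural reading, and overlap, its likely result, has no selection rule

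*Combined protocol and SAP*

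**What the plan says.** Section 6, Specific Aim 3, 3B pools the low FODMAP arm with an earlier diet-treated cohort. The pooled data are "split into a training set from a random sample of 80% of the data while the remaining 20% of the data" form the test set. Then: "Using a random forest model, 5x2 nested cross-validation (CV) will be performed within the training set for model selection and hyperparameter tuning". Candidates are compared as follows: "The candidate models will be compared by testing for overlap of confidence intervals for area under the curves (AUCs, two-sided test". The next step is: "Once a final model is selected, model performance will be evaluated on the test set".

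The documents give no confidence level, no method for the AUC intervals, no list of candidates and no rule for choosing when intervals overlap. Section 10 covers Aims 1 and 2 only, so nothing there fills these gaps.

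**The concern.** Two intervals can overlap while the difference between the two estimates is clearly not zero. The mismatch grows when the estimates are positively correlated, as is likely here: the plan names one learner, a random forest, and all candidates are fitted and scored within one training set. The shared subjects are an inference from the design. The text does not mention pairing, and the size of the correlation is not given.

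Two things follow. First, a real difference between candidates would usually be reported as no difference. Second, when intervals overlap the plan is silent, so the final model would be chosen by an unstated rule after the results are known.

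**Working it through.** **Inputs.** There is no Aim 3 figure in the plan to reproduce.

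- Responder share 60%, from section 10, Aim 2: "we conservatively estimate that 60% of IBS-D subjects will respond to treatment".
- Training share 80%, from section 6, 3B.
- Training size: assumed. The earlier cohort's size is not given, and the diet arm is about 100 (200 subjects at 1:1, section 6) or 32 (section 10: "Given our sample size of 32 subjects per arm, we will have >90% power"). I use 80, 120, 160 and 240, which are 80% of 100, 150, 200 and 300 pooled subjects. With 100 in the arm, 80 is a floor, because the plan does add a cohort.
- Assumed: 95% intervals, true AUCs 0.75 and 0.85, correlation r between the two AUC estimates of 0 or 0.5.

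**Step 1: level with subject-level intervals.** With equal standard errors s, non-overlap needs a difference above 2 × 1.96 × s, while the difference has SD s√(2(1−r)). So level = 2[1 − Φ(3.92/√(2(1−r)))].

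- r = 0: 3.92/1.414 = 2.77, level 0.56%.
- r = 0.5: 3.92/1 = 3.92, level 0.009%.

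The unstated confidence level matters too. At r = 0, 90% intervals give 2.0% and 99% intervals give 0.03%.

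**Step 2: power for 0.75 v 0.85 at r = 0.5.** The Hanley-McNeil standard error is SE² = [A(1−A) + (n1−1)(a−A²) + (n0−1)(b−A²)]/(n1·n0), with a = A/(2−A), b = 2A²/(1+A), n1 responders and n0 non-responders. The difference has SD = √(s1² + s2² − 2r·s1·s2). The overlap rule needs an observed gap of 1.96(s1+s2); a paired test needs 1.96·SD.

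Worked case, 80 subjects (48 responders, 32 non-responders): s1 = 0.0538, s2 = 0.0421, SD = 0.0490.

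- Overlap: gap needed 1.96 × 0.0959 = 0.188; power Φ((0.10 − 0.188)/0.0490) = Φ(−1.79), about 4%.
- Paired: gap needed 1.96 × 0.0490 = 0.096; power Φ(0.10/0.0490 − 1.96) = Φ(0.08) = 53%.

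| Training subjects | Gap needed, overlap | Gap needed, paired | Power, overlap | Power, paired |
|---|---|---|---|---|
| 80 | 0.188 | 0.096 | 4% | 53% |
| 120 | 0.153 | 0.078 | 9% | 71% |
| 160 | 0.132 | 0.068 | 17% | 83% |
| 240 | 0.108 | 0.055 | 39% | 94% |

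In every row the intervals overlap more often than not, although the true gap is 0.10.

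**Step 3: simulation check.** Two sets of correlated scores in 80 subjects, DeLong intervals, score correlation 0.5 (AUC correlation about 0.46), 20,000 runs. With both AUCs at 0.70 the overlap rule rejects 0.04% of the time and the paired DeLong test 5.3%. For 0.70 v 0.80, power is 2.6% v 41%.

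**Step 4: intervals built from folds.** Simulated with fixed scores (no refitting), score correlation 0.5, 2,000 runs per setting.

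- t-intervals over 5 outer folds: the level is at most about 0.25%. AUCs of 0.75 and 0.85 are separated about 3% of the time at 80 subjects, 5–6% at 120, 8–10% at 160 and 16–17% at 240. This is as conservative as Step 2.
- If 5x2 instead means 5 repeats of 2-fold cross-validation, with the 10 fold AUCs treated as independent: the level is about 18–20% at score correlation 0.5 and about 6–8% at 0.8. On this reading the rule is too liberal.

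**Step 5: choosing by highest cross-validated AUC.** P(better model chosen) = Φ(0.10/SD). At r = 0.5 this is Φ(2.04) = 98% with 80 subjects and over 99% with 120 or more.

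**The case against.** Choosing a model needs no hypothesis test, and asking for clear separation can be a deliberate guard against adding complexity on noise. The rule treats both directions alike, so calling it two-sided is fair in that sense, and the plan claims no 5% level that it then breaks. Aim 3 is model development, with performance judged on held-out subjects. All of this stands, and it limits the weight of the point. It does not rescue the rule: a guard against complexity has to say that the simpler model is kept on overlap, and the plan does not.

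Three stronger readings are tempting but not supported.

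- A reader might infer that the false-positive rate is grossly inflated. That needs 5x2 to mean repeated 2-fold cross-validation with its folds treated as independent. The plan says nested, which points to 5 outer and 2 inner folds, where the rule is conservative. The liberal reading is only a secondary reason to replace it.
- A reader might infer that the reported performance of the final model is biased. The test set takes no part in the selection described, so it is not.
- A reader might combine 32 per arm with no earlier data, giving about 26 training subjects and a very small test set. The plan adds a cohort, so that is not a reading of it. The arm-size conflict and the test-set size are separate from this defect.

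**Conclusion.** The point holds as a stated rule that works poorly, and it goes beyond missing detail. With 5 outer and 2 inner folds and 95% intervals, the overlap rule has a level far below 1%. For 0.75 v 0.85 at AUC correlation 0.5 it has 4% to 39% power over 80 to 240 training subjects, where a paired comparison has 53% to 94%. These sizes rest on assumed values for the confidence level, correlation, AUCs and training size; the 60% responder share is the plan's own. The direction does not depend on training size within this range.

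The consequence is confined to which Aim 3 model is kept and to any statement that one beats another. Neither the held-out AUC nor the primary outcome is affected. Worth changing, at the low end of priority.

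**What to change.** Replace the comparison sentence in section 6, 3B with: 'Candidate models will be evaluated on identical folds. The final model is the candidate with the highest cross-validated AUC. Any statement that one model is better than another will rest on the paired difference in AUC from the same out-of-fold predictions, with a 95% CI (DeLong or bootstrap over subjects).' State that 5x2 means 5 outer and 2 inner folds, if that is intended.

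The cost is wording and little computing; no new data are needed. There are three drawbacks. The paired interval treats the fitted models as fixed, so its level is approximate. The highest-AUC rule may favour a more complex model on a trivial gain; a simplicity tie-break stated in advance would deal with that. The winner's cross-validated AUC is optimistic, so only the held-out AUC should be quoted as performance.
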